1.3.4 Rationale for Protocol REL-1017-202

In summary, preclinical and clinical data suggest that low doses of NMDA receptor antagonists such as ketamine initiate brain plasticity processes and increase prefrontal connectivity, reversing the potential effects of chronic stress and depression. The elucidation of these processes, however, has been derived from animal research. There remains a need for research with depressed human subjects to determine if these putative mechanisms of action involving the NMDA receptor and downstream pathways mediate ketamine’s antidepressant effects in depressed patients.

The pre-clinical and previous clinical experience with REL-1017 (d-methadone) provided the basis for the initiation of the present study, which will extend the evaluation of the safety, tolerability, and PK of REL-1017 at 2 doses with repeated administration to humans. Since REL-1017 is proposed for use as adjunctive therapy in the treatment of patients diagnosed with MDD, the patients will be adults with MDD who are diagnosed with a current MDE and who have experienced an inadequate response to 1 to 3 courses of treatment with an adequate dose and duration (as defined by the Antidepressant Treatment Response Questionnaire [ATRQ]) of an antidepressant medication for the current episode will be randomized to study drug in a 1:1:1 ratio. This population will provide the opportunity to compare the safety and efficacy effects of treatment with an antidepressant plus REL-1017 versus the effects of an antidepressant alone.

2 STUDY OBJECTIVES

2.1 Primary Objective

The primary objective of this study is safety:

Safety objectives will assess the safety and tolerability of 25 mg and 50 mg of REL-1017 (d-methadone) compared to Placebo as adjunctive treatment in patients with MDD. The following assessments will be conducted to measure safety and tolerability throughout the study:

- AEs
- Vital signs
- Weight
- Physical examination
- Clinical laboratory parameters (chemistry, hematology, and urinalysis)
- Electrocardiogram (ECG) parameters
- Columbia-Suicide Severity Rating Scale (C-SSRS)
- Clinician Administered Dissociative States Scale (CADSS)
- Clinical Opiate Withdrawal Scale (COWS)
- 4-Item Positive Symptom Rating Scale (4-Item PSRS)

2.2 Secondary Objectives

The secondary objectives of this study are:

2.2.1 Pharmacokinetics:

The PK objective will characterize the PK profile of 25 mg and 50 mg of REL-1017 (d-methadone) as adjunctive treatment in patients with MDD. The PK profile of REL-1017 25 mg and 50 mg will be evaluated on Day 1 through Day 7, Day 8, Day 9, and Day 14 where the data allow:

- Maximum observed plasma concentration (C_{max})
- Time to maximum observed plasma concentration (T_{max})
- Area under the plasma concentration-time curve from time zero until the dosing interval of 24 hours (AUC_{tau})
- Area under the plasma concentration-time curve from time zero until the last quantifiable time point (AUC_{0-last}) on Day 7
- Area under the plasma concentration-time curve from time zero to infinity (AUC_{0-inf})
- Apparent termination elimination rate constant (λ_z)
- Apparent terminal elimination half-life ($t_{1/2}$)

- Attainment of steady state
- Steady state clearance (C_{SS}/F)
- Volume of distribution at steady state (V_{SS}/F)
- Accumulation ratios based on minimum observed plasma concentration (C_{min}), C_{max} , and AUC_{τ}

2.2.2 Efficacy:

The efficacy of 7 days of daily dosing with REL-1017 25 mg and 50 mg will be measured with the following efficacy endpoints:

- Change from Baseline (Day 1) to End of the Dosing Period (EDP, Day 7) on the Montgomery-Asberg Depression Rating Scale (MADRS) with measurements made pre-dose on Day 1 and Day 2; post-dose on Day 4 and Day 7 within 3 hours of dosing; and on Day 14;
- Change from Baseline (Day 1) to EDP (Day 7) on the Symptoms of Depression Questionnaire (SDQ) with measurements made pre-dose on Day 1 and Day 2; post-dose on Day 4 and Day 7 within 3 hours of dosing; and on Day 14; and,
- Change from Baseline (Day 1) to EDP (Day 7) on the Clinical Global Impressions of Severity (CGI-S) with measurements made pre-dose on Day 1 and Day 2; post-dose on Day 4 and Day 7 within 3 hours of dosing; and on Day 14.
- Evaluation of Clinical Global Impressions of Improvement (CGI-I) total score on Day 7 (post-dose), as well as CGI-I scores on Days 2 (pre-dose), 4 (post-dose), and 14.

3 INVESTIGATIONAL PLAN

3.1 Study Design

This a Phase 2a, multicenter, randomized, double-blind, Placebo-controlled 3-arm study to assess the safety and tolerability of multiple oral doses of REL-1017 25 mg and 50 mg as adjunctive therapy in the treatment of patients diagnosed with MDD. The patients will be adults with MDD who are diagnosed with a current MDE who have experienced an inadequate response to 1 to 3 courses of treatment with an antidepressant medication. This population will provide the opportunity to compare the safety and efficacy of REL-1017 with SSRIs, SNRIs, or bupropion versus an antidepressant with Placebo.

The study will be conducted at approximately 10 sites in the United States.

Approximately 60 qualified patients will be randomized to 25 mg or 50 mg of REL-1017 or Placebo with approximately 20 patients per treatment group. REL-1017 will be provided as a powder and will be prepared as a solution with Ocean Spray® Diet Cranberry Juice on site to obtain a final volume of 100 mL for dosing.

An unblinded pharmacist will assign study drug patients according to randomized treatment codes provided by a statistician who is not working as a statistician on the study in any other capacity. The study drug solution will be prepared within 3 hours of administration in blinded containers, and then will be dispensed to blinded study staff for administration to the patients.

The administration of study drug must be observed by a staff member. After drinking the 100 mL of study drug, 25 mL of non-carbonated water will be added to the study drug container and gently swirled. The patient will drink this rinse volume followed by 125 mL of non-carbonated water to drink immediately thereafter. All dosing must be completed within 5 minutes.

Dosing will take place once daily in the morning after an overnight fast.

3.2 Study Procedures

The overall duration of the study will be up to 51 days per patient. All patients will be admitted to the clinical research unit (CRU) for a period of approximately 10 days during which they will receive daily doses of REL-1017 or Placebo for 7 consecutive days. The Screening Visit will assess patient eligibility to participate in the study and will occur between Day -30 and Day -2. Patients will be admitted the day prior to receiving the study drug (Day -1) and will remain in the CRU under clinical supervision for at least 48 hours after the last dose is received on Day 7. Patients will be discharged on Day 9, but return to the CRU 7 days after their last dose of study drug for follow-up evaluations. The study personnel will telephone each patient 14 days after the last dose of study drug and conduct a Follow-Up interview to assess the patient's condition.

The patient's eligibility assessment will be reviewed by an external medical team based on key protocol inclusion and exclusion criteria to promote appropriate patient enrollment and data quality. Sites should submit specific Screening information (detailed in the Massachusetts Clinical Trials Network and Institute [MGH CTNI] manual) within 72 hours after the Screening

[figure not shown]
Visit for review by the external medical team prior to proceeding to Check-in. Subjects who are deemed eligible by the Principal Investigator and confirmed by the Medical Monitor will undergo the SAFER Interview³⁰ by clinicians at the MGH CTNI. To ensure that appropriate subjects are entered into the study, a remote interview will be conducted by MGH CTNI raters. The assessments administered will be the SAFER Interview, which will include the HAM-D17, and the MGH ATRQ. The interview will be performed remotely by the MGH CTNI rater, and the subject will be contacted at his or her home or other off-site location after the Screening Visit, during which call the above assessments will be performed. Sites will be notified of the results within 24 hours of the interview. Only subjects whose eligibility will be confirmed by the SAFER Interview will be allowed to proceed in the study.

The study design is summarized in [Figure 2](#). Study assessments will be performed at the visits and time points outlined in the Time and Events Schedule ([Table 1](#)).

Approximately 60 qualified patients will be randomized to study drug in a 1:1:1 ratio. Arm 1 will consist of approximately 20 patients who will receive REL-1017 25 mg. Arm 2 will consist of approximately 20 patients who will receive REL-1017 50 mg. Arm 3 will consist of approximately 20 patients who will receive Placebo. REL-1017 will be provided as a powder and prepared as a solution with Ocean Spray[®] Diet Cranberry Juice on site to obtain a final volume of 100 mL for dosing. The study drugs will consist of the following:

- Arm 1: REL-1017 (d-methadone) 75 mg of powder in 100 mL of Ocean Spray[®] Diet Cranberry Juice QD on Day 1, 25 mg of powder in 100 mL Ocean Spray[®] Diet Cranberry Juice QD on Day 2-7.
- Arm 2: REL-1017 (d-methadone) 100 mg of powder in 100 mL of Ocean Spray[®] Diet Cranberry Juice QD on Day 1, 50 mg of powder in 100 mL Ocean Spray[®] Diet Cranberry Juice QD on Day 2-7.
- Arm 3: Placebo = 100 mL Ocean Spray[®] Diet Cranberry Juice.

Figure 2: Flow Chart of Study Design

3.3 Discussion of Study Design

Adult patients with MDD who are diagnosed with a current MDE and who have experienced an inadequate response to 1 to 3 courses of treatment with an adequate dose and duration (as defined by the ATRQ) of an antidepressant medication for the current episode will be randomized to study drug in a 1:1:1 ratio. This population will provide the opportunity to compare the safety and efficacy of REL-1017 with SSRIs, SNRIs, or bupropion versus an antidepressant with Placebo.

The randomized, double-blind, Placebo-controlled study is a scientifically valid design for an early Phase 2 study, and the Patient Identification (ID) Numbers are appropriate for the exploratory nature of this study.

The timing of the continuous monitoring and confinement are based on the clinical information of the respiratory depression and other effects as described above (see Section 1).

4 STUDY POPULATION

4.1 Number of Patients

Adult patients with MDD who are diagnosed with a current MDE and who have experienced an inadequate response to 1 to 3 courses of treatment with an adequate dose and duration (as defined by the ATRQ) of an antidepressant medication for the current episode will be randomized to study drug in a 1:1:1 ratio. Approximately 20 patients each will receive REL-1017 75 mg/REL-1017 25 mg, REL-1017 100 mg/REL-1017 50 mg, or Placebo.

Investigators should strive to evenly distribute the choice of ADTs at their respective sites among different ADTs. No more than 2 out of every 6 patients at an investigational site should be assigned to any 1 ADT without permission by the Medical Monitor.

Approximately 120 patients will be screened, and approximately 60 qualified patients will be randomized to study drug in a 1:1:1 ratio (approximately 20 patients per arm). Each patient will participate for up to 51 days (30 days Screening, 7 days treatment, and 14 days of observation and follow-up).

4.2 Inclusion Criteria

Patients will be considered eligible to participate in this study if each of the following inclusion criteria is satisfied at Screening:

1. Males and females between 18 and 65 years of age, inclusive.
2. Diagnosed with recurrent MDD as defined by the Diagnostic and Statistical Manual, Fifth Edition (DSM-5), and confirmed by the Mini International Neuropsychiatric Interview, Version 7.0.2 (MINI).
3. Diagnosed with a current MDE lasting 8 weeks to 36 months as defined by the DSM-5 and confirmed by the MINI.
4. Treated with an adequate dosage of a selective serotonin reuptake inhibitor (SSRI), serotonin and norepinephrine reuptake inhibitor (SNRI), or bupropion during the current MDE for at least 8 weeks prior to Screening with the same, adequate dosage for the last 4 weeks. Minimum adequate doses are defined in the (ATRQ). The maximum dose allowed for paroxetine is 40 mg QD, for fluoxetine is 60 mg QD, and for sertraline is 200 mg QD.
5. Have experienced an inadequate response to 1 to 3 courses of treatment with an antidepressant medication in the current episode, as defined as <50% improvement with an antidepressant medication at doses listed on the SAFER Interview (Criteria: **S**tate versus trait; **A**ssessability; **F**ace validity; **E**cological validity; and **R**ule of three Ps [pervasive, persistent, and pathological]).
6. Hamilton Depression Rating Scale-17 (HAM-D-17) ≥ 19 at Screening and Check-in (Day -1).
7. Body Mass Index (BMI) between 18.0 and 35.0 kg/m², inclusive, and a minimum weight of 50.0 kg.

8. Per the Investigator's judgment, able to meet all study requirements, including the confined/inpatient portion of the study, adherence with both approved ADT and study drug regimen, and completion of all assessments and all scheduled visits.
9. Male and female patients of reproductive potential must be using and willing to continue using medically acceptable contraception, as specified in Section 4.4.2, from Screening and for at least 2 months after the last study drug administration. Female patients must have a negative pregnancy test, and must not be lactating.
10. Must be able to read, speak, and understand English and must provide written informed consent prior to the initiation of any protocol-specific procedures.

4.3 Exclusion Criteria

Patients will not be considered eligible to participate in this study if any one of the following exclusion criteria is satisfied at Screening:

1. History or presence of clinically significant abnormality as assessed by physical examination, medical history, 12-lead ECG, vital signs, or laboratory values, which in the opinion of the Investigator would jeopardize the safety of the patient or the validity of the study results, including torsades de pointes, any bradyarrhythmias, or uncompensated heart failure.
2. Chronic use of prescribed opioids (i.e., >120 days in a 6-month period) up to 6 months prior to Screening or any recreational use of opioids.
3. Evidence of clinically significant hepatic or renal impairment, including alanine aminotransferase (ALT) or aspartate aminotransferase (AST) >1.5 x upper limit of normal (ULN), bilirubin >1 x ULN, or endocrine laboratory values (including clinically significant thyroid parameters, i.e., thyroid stimulating hormone [TSH], triiodothyronine [T3], and thyroxine [T4]).
4. History or family history of sudden unexplained death or long QT syndrome (measure of the time between the start of the Q wave and the end of the T wave in the heart's electrical cycle).
5. An average QTcF \geq 450 msec or an average QRS interval \geq 120 msec from the 12-lead ECGs performed at Screening.
6. History of clinically diagnosed hypotension requiring treatment.
7. History or presence of any condition in which an opioid is contraindicated (e.g., significant respiratory depression, acute or severe bronchial asthma or hypercarbia, bronchitis, or has/is suspected of having paralytic ileus).
8. No more than 3 prescribed doses of an opioid within the 6 months prior to Screening and no use at all within the last month.
9. Use of an antipsychotic, anticonvulsant, or mood stabilizer, regardless of indication, within the 3 months prior to Screening.

10. History of allergy or hypersensitivity to methadone or related drugs (e.g., opioids).
11. Positive test for hepatitis B or human immunodeficiency virus (HIV). Patients with a positive hepatitis C test may be considered for inclusion with approval from the Medical Monitor.
12. Any current and primary psychiatric disorder, as defined as a condition that is the primary focus of distress and/or treatment, other than MDD.
13. Any lifetime history of bipolar I or II disorder, any psychotic disorder, post-traumatic stress disorder, borderline personality disorder, antisocial personality disorder, obsessive compulsive disorder, eating disorder, intellectual disability, or pervasive developmental disorder.
14. History in the past 12 months of a primary diagnosis of anxiety disorder or panic disorder not related to the current MDE.
15. Current diagnosis of alcohol or substance use disorder, as defined by DSM-5, at Screening or within the 12 months prior to Screening. Patients with the following diagnoses within the past 12 months, however, may be included at the Investigator's discretion: mild alcohol use disorder, mild cannabis use disorder, and any severity tobacco use disorder.
16. A confirmed positive result on the urine drug/alcohol screen at Screening or Check-in. If the urine drug/alcohol screen is positive at Screening, retesting or rescreening may be scheduled with prior approval from the Medical Monitor.
17. Patients who, in the Investigator's judgment, are at significant risk for suicide. A patient with a Columbia-Suicide Severity Rating Scale (C-SSRS) ideation score of 4 or 5 within the last 6 months or any suicide attempt within the past year must be excluded, as should a patient with an ideation score of 4 or 5 or any suicide attempt at the Check-in or Baseline Visit.
18. Patients with a 20% improvement between Screening and Check-in (Day -1) on the HAM-D-17.
19. Patients who did not safely discontinue medications prohibited in Section 4.4.1.
20. Patients receiving new onset psychotherapy (individual, group, marriage, or family therapy) within 2 months prior to Screening or plans to start at any time during participation in the study.
21. Patients who have received electroconvulsive therapy (ECT), repetitive transcranial magnetic stimulation (rTMS), or vagus nerve stimulation (VNS) or who have participated in a ketamine study within the last 6 months.
22. Patients with any clinically significant neurological, hepatic, renal, metabolic, hematological, immunological, cardiovascular, pulmonary, chronic pain, or gastrointestinal disorder. Medical conditions that are minor or well-controlled may be

permitted if they will not increase the safety risk to the patient or compromise interpretation of the safety or efficacy endpoints.

23. Patients taking fluvoxamine or St. John's Wort.
24. Patients who have participated in a clinical study with an investigational medication in the past 6 months, or who have participated in more than 4 clinical studies with investigational medications in the past 2 years.

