6.1.2 Check-In (Day -1)

Inpatient admission may occur up to 30 days after the Screening Visit as soon as it is determined that patients meet all Screening criteria. Upon Check-in, patients will undergo further medical and psychiatric Screening according to the Time and Events Schedule (Table 1) to ensure they continue to qualify for participation in the study. The patient's prescribed antidepressant will be administered by site personnel while the patient is confined to the study unit.

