6.2.5.8 Pregnancy Testing

A urine pregnancy test and a serum follicle stimulating hormone (FSH) test will be administered to all female patients at Screening (Day -30 to Day -2). Negative test results are required for enrollment in the study. Another negative urine pregnancy test will be required at Check-in (Day -1) for confirmation. Additional confirmatory pregnancy tests will be administered at the End of the Observation Period Visit (Day 14 ± 3 days and Follow-Up Visit (Day 21 ± 3 days).

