8.1.5 Demographics and Other Baseline Characteristics

Demographics and Baseline characteristics (age, sex, race, ethnicity, body weight, height, oral body temperature, and BMI) will be summarized using descriptive statistics (number of patients, mean, SD, median, minimum, and maximum for continuous variables and the proportion of patients for categorical variables) for the Safety population. No formal statistical comparison between the groups will be performed. Demographics and height will be recorded at Screening only. Weight and oral body temperature will also be recorded at Check-in (Day -1), EDP (Day 7), and EOP (Day 14). In addition, BMI will be calculated at Screening.

The patient's eligibility for participation in the study will be determined with the inclusion and exclusion criteria at Screening. The inclusion and exclusion criteria will be reviewed again at Check-in (Day -1) when the patient is admitted to the CRU. The study restrictions review will also occur at Check-in (Day -1).

Patients will be confined to the CRU from Check-in (Day -1) through Discharge on Day 9. Patients will be administered study drug daily from Day 1 through Day 7.

Randomization will occur on Day 1 prior to administration of the first dose of study drug. The treatment assignment for each patient will be assigned through the IWRS in a 1:1:1 ratio (REL-1017 25 mg, REL-1017 50 mg, or Placebo), and the randomization schedule will be stratified based on patients receiving concomitant ADTs that are cytochrome (CYP) 2B6 inhibitors (e.g., paroxetine, fluoxetine) versus those who are not.

Medical history and psychiatric history will be coded into the most recent version of MedDRA available (Version 16.0 or higher). Medical history will be listed by treatment arm and patient at

Screening and Check-in (Day -1). Psychiatric history will be listed by treatment arm and patient at Screening only.

Prior and concomitant medications will be assigned a 12-digit code using the most recent version of the WHO drug codes available. Prior and concomitant medications will be listed by treatment arm and patient. Medication history (prior medications) will be listed at Screening, and concomitant medications will be listed at every visit from Check-in (Day -1) through EOP (Day 21) and summarized by treatment.

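### The QTcF and QRS entry limits apply only to the Screening ECGs, so the Check-in ECG taken the day before the loading dose has no numeric limit

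*Combined protocol and SAP*

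**What the plan says.** Exclusion 5 sets two limits, average QTcF at or above 450 and average QRS at or above 120, "msec from the 12-lead ECGs performed at Screening". The stem of Section 4.3 excludes a patient "if any one of the following exclusion criteria is satisfied at Screening".

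Section 6.1.2 separates the visits: "Inpatient admission may occur up to 30 days after the Screening Visit". At Check-in, patients have further medical and psychiatric assessment "to ensure they continue to qualify for participation in the study". Table 1 and Section 8.1.5 place a second review of the eligibility criteria on Day -1, and Section 6.1.3 requires a Baseline checklist on Day 1 before randomization. The checklist's content is not given.

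Section 6.2.4 schedules triplicate ECGs at Screening, at Check-in and 1 hour before dosing on Day 1. It sends ECGs to a central reader for evaluation for study entry and leaves the final judgment on the entry criteria to the Investigator. It states no QTcF or QRS limit for any visit.

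**The concern.** Reviewing Exclusion 5 again at Check-in, as it is worded, leads back to the Screening tracing, which may be a month old. The newer Check-in triplicate is taken, but nothing in the text says what value on it excludes a patient. Read literally, the protocol lets a patient receive the loading dose when the latest eligibility ECG is above the sponsor's own entry limit.

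Three features make this worth correcting. Safety is the primary objective. Day 1 carries the highest dose in both active arms (75 mg or 100 mg). Section 1.1.1 reports hERG block by d-methadone, with an IC50 of 2 µM against 7 µM for l-methadone. With about 10 sites, a criterion left to judgment may also be applied differently from site to site.

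**Working it through.** **Text comparison.** The question is which visits carry a written requirement.

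| Criterion | Later visit named? |
|---|---|
| Inclusion 6 (HAM-D-17 of 19 or more) | Yes, Check-in |
| Exclusion 16 | Yes: "A confirmed positive result on the urine drug/alcohol screen at Screening or Check-in" |
| Exclusion 17 (C-SSRS) | Yes, Check-in or Baseline |
| Exclusion 18 (HAM-D-17 improvement) | Yes, Check-in |
| Inclusion 9 (pregnancy test) | Not there, but Section 6.2.5.8 adds: "Another negative urine pregnancy test will be required at Check-in (Day -1) for confirmation" |
| Exclusion 5 (QTcF, QRS) | No, Screening only |

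**Other rules that could act on the Check-in ECG**

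- Exclusion 1 depends on the Investigator's opinion, and Exclusion 22 needs a clinically significant disorder.
- Section 4.5 allows discontinuation for a clinically significant ECG abnormality as assessed by the Investigator or designee.
- The numeric rule in Section 4.5 is QTcF of 500 msec or more, or 60 msec or more above Baseline. Section 7.1.4 places the QTcF Baseline on Day 1, so the 60 msec part cannot govern a Check-in ECG. The 500 msec part arguably can. There is no QRS limit.

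What remains to judgment at Check-in is QTcF 450-499 msec and any QRS of 120 msec or more.

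**Size (illustration only).** The documents give no QTcF distribution, so every input here is assumed: population mean μ = 405, 410, 415 or 420 msec; between-patient SD σb = 15, 16.5 or 18; within-patient SD of a triplicate mean σw = 7, 8.5 or 10. That is 4 × 3 × 3 = 36 settings.

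Model: the patient's true mean is T ~ N(μ, σb²). Each visit's triplicate average is T plus independent N(0, σw²) error, with no systematic shift between visits. Let p(T) = Φ((450 − T)/σw) be the chance of a reading below 450 msec, and let E denote the average over T by numerical integration.

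- First at 450 or more at Check-in, having passed Screening: E[p(1 − p)] / E[p] = 0.00215 to 0.03980. Times 60: 0.13 to 2.39. Times 40 (active arms): 0.09 to 1.59.
- Of these, 77% to 93% read 450-459 msec, and 71% to 94% have a true mean below 450.
- Newly at or above the limit with a true mean of 450 or more: 0.00026 to 0.00903. Times 60: 0.02 to 0.54.
- At 470 or more at Check-in: at most 0.00140. Times 60: 0.08.
- Day 1 pre-dose at 450 or more, present text: the same expression as for Check-in, 0.13 to 2.39 of 60.
- Day 1 pre-dose at 450 or more, once Check-in is added: E[p²(1 − p)] / E[p²] = 0.00167 to 0.02827. Times 60: 0.10 to 1.70. The ratio to the present text within a setting is 0.66 to 0.84, a reduction of 16% to 34%.
- Late failures if Day 1 pre-dose is added as well: E[p(1 − p²)] / E[p] = 0.00382 to 0.06694. Times 60: 0.23 to 4.02.

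The lowest patient counts come from (μ, σb, σw) = (405, 15, 7) and the highest from (420, 18, 10). At one mid-range setting (410, 16.5, 8.5), 0.58 of 60 exceed the limit at Check-in, and the Day 1 figure falls from 0.58 to 0.43 of 60. QRS was not modelled.

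**The case against.** The strongest reply is that the protocol already deals with this. Check-in is described as further screening, the criteria are reviewed again that day, and a Day 1 checklist asks whether the patient is still eligible. A sensible site would hold the current ECG against the limits. The stem's reference to Screening also heads Exclusions 16 to 18, which use later findings, so it is not a strict restriction. The table of changes for Amendment 4 shows that this criterion was rewritten and kept Screening, which could be deliberate. The Investigator's final judgment on entry ECGs covers Screening as well.

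Part of this stands. Sites may already apply the limits, and the stem alone proves little. But nothing requires them to do so. Exclusion 5 carries its own visit restriction apart from the stem, and no reason is given for leaving a scheduled triplicate without a limit.

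The second reply is that the practical risk is small. That also stands:

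- Patients are confined from Day -1 to Day 9.
- Triplicate ECGs follow at 2, 4, 6 and 8 hours on Days 1 and 2, and daily after that.
- A cardiologist reviews stopping-rule findings.
- Exclusion 4 removes personal or family long QT syndrome.
- Phase 1 in healthy subjects reported no QT prolongation at single doses up to 200 mg, twice the larger loading dose.

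Most patients caught by the change would be near the limit through ordinary variability, and the change would not guarantee the Day 1 starting value. These points limit the importance of the gap but do not close it.

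**Conclusion.** The concern holds as a minor safety clarification. The written QTcF and QRS entry limits reach only the Screening ECGs, and at Check-in QTcF 450-499 msec and QRS of 120 msec or more are left to Investigator judgment. That conclusion rests on the text alone.

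Its size rests on assumed QTcF inputs: roughly 0 to 2 patients in 60 affected, and about half a patient at most whose true average is at or above the limit. A real change between visits, for example from a change in medication, is outside that model. The benefit is that the sponsor's own limit would apply to a recent ECG, in the same way at every site, before the largest dose.

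**What to change.** In Section 4.3 and the Synopsis, extend the end of Exclusion 5 to cover the 12-lead ECGs at Screening or at Check-in (Day -1), with the same limits and the triplicate average.

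The cost is one phrase in two places. The Check-in triplicate is already scheduled and the ECG calculates QRS and QTc electronically (Section 6.2.4), so no new assessment is needed and the sample size does not change. The downside is about 0 to 2 late screen failures in 60 on the assumed inputs, after the SAFER interview and admission, mostly within 10 msec of the limit. The sponsor may wish to state whether a borderline value can be repeated and which reading decides.

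Fixing the starting value itself would mean applying the limits to the Day 1 pre-dose ECG too. I would not recommend that: on the same inputs late failures rise to 0.23-4.02 of 60, again mostly from ordinary variability.
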